### **8.2 Data collection**

Designated Investigator staff will enter the data required by the protocol into the eCRF using fully validated software that conforms to US CFR 21Part 11 requirements. Designated Investigator site staff will not be given access to the eCRF system until they have been trained. Automatic and manual validation programs check for data discrepancies and, by generating appropriate error messages, allow the data to be confirmed or corrected before transfer of the data to the CRO working on behalf of Novartis. The Investigator must certify that the data entered into the eCRF are complete and accurate. After database lock, the Investigator will receive copies of the patient data from the CRO for archiving at the investigational site.

### **8.3 Database management and quality control**

Novartis staff and staff at a CRO working on behalf of Novartis will review the data entered into the eCRFs by investigational staff for completeness and accuracy and instruct the site personnel to make any required corrections or additions. Queries are sent to the investigational site using an electronic data query. Designated Investigator site staff are required to respond to the query and confirm or correct the data. All relevant comments should be added to the eCRF using the Investigator Comment feature.

Concomitant medications entered into the database will be coded using the WHO Drug Reference List, which employs the Anatomical Therapeutic Chemical (ATC) classification system. Medical history/current medical conditions and adverse events will be coded using the Medical dictionary for regulatory activities (MedDRA) terminology.

Data about the study drug dispensed to the patient will be tracked using the eCRF. The eCRF system will be supplied by a CRO, who will also manage the database.

OCT, color fundus photographs, fluorescein angiograms, ICGA and fundus autofluorescence images will be processed centrally by the CRC and the results will be sent electronically to a designated CRO for incorporation into the master database. Data management staff will perform a reconciliation of the data entered into the eCRF versus what is received from the CRC. At a minimum, this reconciliation will include header reconciliation, visit window checks, duplicate record checks, out-of-range checks as defined by the Clinical Trial Team and checks to address missing reading center data.

At the conclusion of the study, the occurrence of any protocol deviations will be determined. After these actions have been completed and the database has been declared to be complete and accurate, it will be locked. Following database lock, the database will be sent electronically to Novartis (or a designated CRO). Any changes to the database after that time can only be made by joint written agreement by the Clinical Trial Leader, the Trial Statistician, the Data Manager and the Quality Manager.

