### **5.4 Treatment masking**

This is an open-label study and neither Investigators nor patients are masked.

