## 9 Data analysis

The statistical analysis will be performed by staff at a CRO working on behalf of Novartis.

There will be one interim analysis after the first 50 patients have completed all visits up to Day 90 (see section 9.6) and the final analysis after all patients have completed the study.

Descriptive statistics include n (the number of non-missing values), mean, standard deviation, median, minimum, maximum and, where appropriate, confidence intervals for continuous variables and frequencies and percentages for categorical variables and will be provided where applicable for patients and study eye. All data will be listed by patient, and where applicable, by eye.

For statistical purposes, baseline will be defined as the last available non-missing value collected just prior to the start of treatment in the study eye.

For patients with screening assessments who do not enter the treatment period, data will only be listed. For patients who do not enter the treatment period due to a study eye specific exclusion criterion, descriptive statistics as described above will be provided.

Unless otherwise specified, all statistical tests will be two-sided and use the 0.05 level of significance.

Further technical details and discussion of the following statistical considerations will appear in the Statistical Analysis Plan, which will be finalized prior to database lock and the analysis.

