### 9.1 Analysis sets

For all patients only one eye will be considered as the study eye, but efficacy and safety parameters will be recorded for both eyes. In the event that a subject develops visual impairment due to nAMD in the fellow eye (non-study eye) during the study which is treated at the Investigator's discretion according to the standard of care, any additional data (except for BCVA, ranibizumab injections and AEs and SAEs that occur in the fellow eye) collected according to routine practice will not be recorded on the eCRF. Data presentations will distinguish study and fellow eye values.

The **Full Analysis Set (FAS)** will consist of all patients who received at least one application of study treatment in the study eye, have baseline and have at least one post-baseline assessment for CSRT. Following the intent-to-treat principle, patients will be analyzed according to the treatment assigned. No data will be excluded from the FAS analyses because of protocol deviations.

The **Per Protocol Set (PPS)** will consist of all patients in the FAS who followed the assigned treatment and completed the study without clinically significant protocol deviations. Clinically significant protocol deviations will be defined in the Statistical Analysis Plan. If deviations do occur, then the data from specific patients, visits, or evaluations may be excluded from the PPS. The criteria and determination of clinically relevant protocol deviations and patient specific identification of data to be excluded from the PPS will be databased and finalized prior to database lock.

The **Safety Set (SAF)** will consist of all patients who received at least one application of study treatment in the study eye and had at least one post-baseline safety assessment. The statement that a patient had no adverse events also constitutes a safety assessment.

All efficacy evaluations will be carried out on the Full Analysis Set and all safety evaluations will be carried out on the Safety Set.

For sensitivity purposes, the primary analysis will be repeated using the Per Protocol Set. Any major discrepancies in the results across analyses will be investigated as necessary.

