2.1 Patients and treatments

2.1.1 Analysis sets

Assignment of patients to analysis sets will be agreed between the study statistician and the Sponsor prior to database lock, once all study data are available and verified. All efficacy analyses will be performed on the study eye. For visual acuity tests, the results for the fellow eye (non-study eye) will also be summarized for reference.

Full Analysis Set (FAS): The FAS consists of all patients who received at least one application of study treatment in the study eye, have baseline and have at least one post-baseline assessment for CSRT. Following the intent-to-treat principle, patients will be analyzed according to the treatment assigned. No data will be excluded from the FAS analyses because of protocol deviations.

Per Protocol Set (PPS): The PPS consists of all patients in the FAS who followed the assigned treatment and completed the study without clinically significant protocol deviations.

Safety Set (SAF): The SAF consists of all patients who received at least one application of study treatment in the study eye and had at least one post-baseline safety assessment.

All efficacy evaluations will be carried out on the Full Analysis Set and all safety evaluations will be carried out on the Safety Set. For sensitivity purposes, the primary analysis will be repeated using the Per Protocol Set. Any major discrepancies in the results across analyses will be investigated as necessary.

In addition, 2 subgroups of patients are defined:

- Group 1. Primary treatment failure (PTF)
- Group 2. Suboptimal treatment response (STR)

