2.1.3 Protocol deviations

Protocol deviations (PDs) are collected as per the latest version of the VAP Module 3 - Protocol Deviations (see Appendix 2). This document gives a full list of possible PDs, including whether they are programmatically or manually derived, as well as Severity/Analysis classification codes to be assigned to each PD. Rules for patient classification in the analysis sets based on PDs are as follows:

Protocol deviations and impact on analysis

Code	VAP de-code	Impact on analyses
0	Exclude from all efficacy analysis (including ITT)	Exclude patient completely from the FAS and Per-Protocol Sets.
1	Exclude from Per-Protocol analysis	Exclude patient completely from Per-Protocol Set.
2	Exclude from data analysis from this date	Data from this date/visit onwards excluded from per protocol analyses (patient not excluded from population).

49 Report relevant protocol deviation – Include in all analysis
include in all analyses

A protocol deviation meeting will be organized. The criteria and determination of clinically relevant protocol deviations and patient specific identification of data to be excluded from the PPS following this meeting will be databased and finalized prior to database lock.

All protocol deviations will be listed. All responses to the screening and baseline log will also be listed.

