2.5 Interim analysis

[figure not shown]
An interim analysis will be conducted after the first 50 patients have completed visits up to Day 90. This will be used primarily to provide preliminary data on the safety of ranibizumab in patients with nAMD with either primary treatment failure or suboptimal treatment response to aflibercept. The results from this Day 90 analysis will be submitted for publication. As no hypothesis tests will be carried out, no statistical adjustments are required.

Descriptive analyses will be carried out on the main safety and efficacy variables, as follows:

[figure not shown]
- Demographics and baseline characteristics
- Adverse events – All summary tables and listings mentioned in Section 2.4.1
- Primary efficacy variable
- Secondary efficacy variables – All summary tables and listings mentioned in Section 2.2.2.
- 

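### Per-protocol exclusions are settled at a late meeting with nothing stated to keep CSRT from those deciding, and SAP code 0 lets a deviation reach the primary FAS that both documents say is immune

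*Protocol*

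**What the plan says.** **Timing.** Protocol 8.3 sends the reading centre's results to a CRO for the master database and describes reconciliation. It then states: "At the conclusion of the study, the occurrence of any protocol deviations will be determined". Lock follows. SAP section 2 also refers to a deviation review at the end of the study. Under SAP 2.1.1 the study statistician and the sponsor agree the analysis sets "prior to database lock, once all study data are available and verified".

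**Criteria.** Protocol 9.1 promises: "Clinically significant protocol deviations will be defined in the Statistical Analysis Plan". Protocol 9 gives the SAP's deadline as "which will be finalized prior to database lock and the analysis". SAP 2.1.3 points to VAP Module 3 in Appendix 2: "This document gives a full list of possible PDs, including whether they are programmatically or manually derived", with an analysis code for each. The same section then describes a deviation meeting. "The criteria and determination of clinically relevant protocol deviations and patient specific identification of data to be excluded from the PPS following this meeting" are to be finalised before lock.

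**Codes (SAP 2.1.3).** Code 0 removes the patient from both the FAS and the PPS. Code 1 removes the patient from the PPS. Code 2 drops data from a given date or visit onwards from per-protocol analyses.

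**Roles of the sets.** The primary analysis uses the FAS and is repeated on the PPS as a sensitivity analysis (Protocol 9.1 and 9.4.4; SAP 2.1.1 and 2.2.1.2). Protocol 9.1 and SAP 2.1.1 both say that deviations lead to no exclusion of data from FAS analyses.

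**Masking.** Protocol 5.4: "This is an open-label study and neither Investigators nor patients are masked". No section describes masking of the people who classify deviations.

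**Interim.** SAP 2.5 lists the primary efficacy variable among the outputs for the first 50 patients. "The results from this Day 90 analysis will be submitted for publication".

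**The concern.** Settling exclusions before database lock protects a masked randomised trial because the reviewers cannot tell which exclusions favour which arm. That protection is absent here. There is one arm, the objective is a mean change below zero, and a patient's own fall or rise in CSRT shows at once whether dropping that patient helps. Lock hides nothing from anyone who can see the values.

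The PPS repeat is the sensitivity analysis named for the primary result. If its exclusions, or the removal of a single Day 90 value under code 2, can be decided with sight of CSRT, agreement between PPS and FAS gives little reassurance. Code 0 adds a second issue: it is a stated route by which the same judgement could reach the primary analysis.

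**Working it through.** The documents give no figure for this point, so the texts are compared first and the possible size is then illustrated.

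**1. What remains open at the meeting.** VAP Module 3 already lists and codes possible deviations, some of them derived manually. SAP 2.1.3 nevertheless makes the criteria, as well as their application to patients, something finalised after the meeting. Those two statements leave an unspecified amount of discretion.

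**2. What the deciders can see.** SAP 2.1.1 puts the decision after all data are available and verified. Protocol 8.1 has sponsor monitors verify data for the primary variables, and the interim outputs will show Day 90 CSRT for the first 50 patients. No section withholds CSRT from the meeting. That it is visible there is an inference from this silence.

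**3. Which analysis is exposed.** The FAS requires one study treatment, a baseline CSRT and one post-baseline CSRT, with no judgement of deviations. The PPS depends on deviations by definition. Code 0 is the only stated link from a deviation to the FAS.

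**4. Size, under assumptions.** Inputs:
- N = 124 (Protocol 4).
- SD of change = 102 µm (figure in the Amendment 2 summary), so SE = 102/√124 = 9.16 µm.
- Assumed: true mean change 0; a share of patients has a reviewable deviation unrelated to outcome; every such patient whose CSRT rose is dropped and every one whose CSRT fell is kept. This is the worst case.

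With k reviewable patients, about k/2 are dropped. Those kept have mean -102 × √(2/π) = -81.4 µm, and the other N - k patients average 0. So

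shift ≈ -81.4 × (k/2) / (N - k/2).

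- k = 6: -81.4 × 3/121 = -2.0 µm
- k = 12: -81.4 × 6/118 = -4.1 µm
- k = 25: -81.4 × 12.5/111.5 = -9.1 µm

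A simulation of 20,000 trials agrees. It also gives the chance that the two-sided 95% interval lies wholly below zero when there is no true change:

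| Share reviewable | k | Simulated shift (µm) | Shift/SE | Chance of a false reduction |
|---|---|---|---|---|
| 0% | 0 | 0.1 | 0.0 | 2.5% |
| 5% | 6 | -2.0 | 0.2 | 4.2% |
| 10% | 12 | -4.0 | 0.4 | 6.1% |
| 20% | 25 | -9.1 | 1.0 | 14.8% |

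With the SAP's enrolment figure of 150 the shifts are -2.3, -4.2 and -9.0 µm and the chances 4.5%, 7.1% and 17.2%. If exclusion is unrelated to outcome, the shift is zero.

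**The case against.** Finalising per-protocol exclusions before lock is usual practice, and several stronger readings go beyond the documents.

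- *All analysis sets can follow the outcome.* A reader might infer this from the late assignment. FAS membership is objective and both documents shield it from deviations; only code 0 breaks the shield.
- *Deviations and criteria appear only at the end.* Some deviations are recorded as they occur, such as a delayed injection (Protocol 5.5.4) or an early repeat injection in the fellow eye (Protocol 5.5.4.3). VAP Module 3 already lists and codes them. Its contents and date are not in the text supplied, so whether its rules predate the interim cannot be checked and should not be held against the plan.
- *The meeting will be shown CSRT.* No document says so. Reading-centre results go to a CRO, and Protocol 8.3 transfers the database to the sponsor or a CRO only after lock.
- *The interim is compromised.* It is descriptive, tests no hypothesis, and SAP 2.5 lists no PPS output. Its relevance is that it shows outcomes while the rules may still be open.
- *The distortion could be much larger.* Dropping the worst 6 or 12 of all 124 patients would shift the mean by about -11 or -19 µm, but only patients with a codable deviation can be excluded.

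Protocol 3.2 also calls the study exploratory and accepts bias from the unmasked design. These points narrow the concern to the PPS and code 0. They do not answer the discretion left to the meeting, the manually derived deviations or the absence of an outcome-blind review.

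**Conclusion.** The point holds in a limited form and is a cheap improvement rather than a threat to the primary result. Final criteria and patient- or visit-level PPS exclusions are settled when all data are available, in a design where the individual CSRT change is the result, with no stated barrier between that result and the deciders. The PPS repeat is therefore weaker support than it appears. The primary analysis is exposed only if code 0 is used, and that code contradicts the FAS rule.

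In the worst case modelled, the shift stays under half a standard error when up to 10% of patients have a reviewable deviation and reaches about one standard error at 20%. Those shares and the wholly outcome-driven exclusion are assumptions with no source in the documents. Any realistic selection would be weaker. The documents do not show that exclusions will follow outcome, only that nothing stated prevents it.

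**What to change.** Amend SAP 2.1.1 and 2.1.3, and Protocol 8.3 to match:

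1. Freeze the VAP Module 3 criteria and codes, with a date, before the 50-patient interim outputs are produced. Limit the end-of-study meeting to applying them. If the module was already final by then, a sentence saying so is enough.
2. Classify deviations and sign off the analysis sets on listings without post-baseline CSRT or other OCT or visual acuity values. Some deviations depend on those values, for example a PRN injection that was required under SAP 2.1.7 but not given. Derive these by program and show them only as flags. Reading-centre reconciliation continues before lock as planned, done by data management staff who take no part in classification.
3. Reconcile code 0 with the FAS definition, so that a deviation cannot remove a patient from the primary analysis.

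The cost is wording in two documents, slightly earlier coding work and some extra programmed listings. No study visit or assessment changes.

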### **8.4 Data Monitoring Committee**

Not applicable.

### **8.5 Adjudication Committee**

Not applicable

## 9 Data analysis

The statistical analysis will be performed by staff at a CRO working on behalf of Novartis.

There will be one interim analysis after the first 50 patients have completed all visits up to Day 90 (see section 9.6) and the final analysis after all patients have completed the study.

Descriptive statistics include n (the number of non-missing values), mean, standard deviation, median, minimum, maximum and, where appropriate, confidence intervals for continuous variables and frequencies and percentages for categorical variables and will be provided where applicable for patients and study eye. All data will be listed by patient, and where applicable, by eye.

For statistical purposes, baseline will be defined as the last available non-missing value collected just prior to the start of treatment in the study eye.

For patients with screening assessments who do not enter the treatment period, data will only be listed. For patients who do not enter the treatment period due to a study eye specific exclusion criterion, descriptive statistics as described above will be provided.

Unless otherwise specified, all statistical tests will be two-sided and use the 0.05 level of significance.

Further technical details and discussion of the following statistical considerations will appear in the Statistical Analysis Plan, which will be finalized prior to database lock and the analysis.

### 9.1 Analysis sets

For all patients only one eye will be considered as the study eye, but efficacy and safety parameters will be recorded for both eyes. In the event that a subject develops visual impairment due to nAMD in the fellow eye (non-study eye) during the study which is treated at the Investigator's discretion according to the standard of care, any additional data (except for BCVA, ranibizumab injections and AEs and SAEs that occur in the fellow eye) collected according to routine practice will not be recorded on the eCRF. Data presentations will distinguish study and fellow eye values.

The **Full Analysis Set (FAS)** will consist of all patients who received at least one application of study treatment in the study eye, have baseline and have at least one post-baseline assessment for CSRT. Following the intent-to-treat principle, patients will be analyzed according to the treatment assigned. No data will be excluded from the FAS analyses because of protocol deviations.

The **Per Protocol Set (PPS)** will consist of all patients in the FAS who followed the assigned treatment and completed the study without clinically significant protocol deviations. Clinically significant protocol deviations will be defined in the Statistical Analysis Plan. If deviations do occur, then the data from specific patients, visits, or evaluations may be excluded from the PPS. The criteria and determination of clinically relevant protocol deviations and patient specific identification of data to be excluded from the PPS will be databased and finalized prior to database lock.

The **Safety Set (SAF)** will consist of all patients who received at least one application of study treatment in the study eye and had at least one post-baseline safety assessment. The statement that a patient had no adverse events also constitutes a safety assessment.

All efficacy evaluations will be carried out on the Full Analysis Set and all safety evaluations will be carried out on the Safety Set.

For sensitivity purposes, the primary analysis will be repeated using the Per Protocol Set. Any major discrepancies in the results across analyses will be investigated as necessary.

### **Defined subgroups**

Two subgroups of the FAS are defined for exploratory analyses (see section 4.1 for full definitions):

- 1) Group 1. Primary treatment failure (PTF)
- 2) Group 2. Suboptimal treatment response (STR)

Analyses to be presented for subgroups in addition to the main analysis sets (FAS or SAF) are indicated below.

## **9.2 Patient demographics and other baseline characteristics**

Descriptive statistics will be provided for patient demographics and all baseline characteristics (including the baseline values of the main efficacy endpoints).

Relevant medical history (ocular and non-ocular) and current medical conditions will be tabulated by system organ class and preferred term of the MedDRA dictionary. Separate tables will be provided for ocular (in study eye and fellow eye) and non-ocular histories and conditions. Other relevant baseline information will be listed and summarized as appropriate with descriptive statistics. Data will be summarized for the FAS and also for the subgroups PTF and STR.

